2.11.7 Laboratory data

See [Appendix 2](#) (Safety laboratory tests: Order of presentation in (international system of units [SI units])) for the list of hematology, clinical and urinalysis tests comprising the safety laboratory assessments.

Blood samples should be recorded after an 8-hour fast. Fasting status (yes/no) at the time of sample collection, will identify those results obtained from samples where the patient has not fasted adequately. For the following laboratory tests sensitive to fasting status, only fasting results will be used for analysis purposes:

- Glucose (mmol/L).
- Cholesterol (mmol/L).
- Lipids (mmol/L).
- Lipase (U/L).

Per [Table 3.3](#) (see [Section 3.5.1](#) [Analysis visit windowing and naming]) the following will be derived:

Baseline (derived) is defined as the last available assessment (scheduled or unscheduled) prior to the start of the first infusion of study drug, including pre-dose assessments at Day 1.

End of Treatment (derived) is defined as the last available assessment (scheduled or unscheduled) assigned to treatment (expected per protocol at Week 20 + 56-days).

End of Study (derived) is defined as the last available assessment (scheduled or unscheduled) assigned to the study.

Analyzable laboratory assessment (per realigned visit window): Assessment closest to the actual target day. If two assessments are separated by the same number of days from the target visit day, the earliest assessment will be used.

Any test results below the limit of quantification will be analyzed as 0.5x the lower limit. Any test results above the limit of quantification will be analyzed as 1.5x the upper limit.

Descriptive statistics (see [Section 3.2](#) [Precision and summary statistics]) for quantitative and qualitative laboratory assessments (hematology, clinical, immunochemistry and urinalysis) will be presented for all patients assigned to the SAF analysis set, at each windowed visit and change from Baseline at each windowed post-baseline visit and End of Treatment (derived)/End of Study (derived), as relevant. All summaries will be presented for each treatment group and across active bimagrumab treatment groups combined (“Active Total: Safety” - Includes bimagrumab 700 mg, bimagrumab 210 mg and bimagrumab 70 mg). All laboratory assessments will be presented overall and region.

The mean change from Baseline in quantitative laboratory assessments at each windowed post-baseline visit including End of Treatment (derived)/End of Study (derived) and the associated 95% confidence interval of the mean will be presented graphically, by treatment group and across all four treatment groups combined, overall only. Only laboratory assessments with a clinically notable criterion as defined in [Section 3.8](#) (Clinically notable values), by laboratory system, and in the order defined in [Appendix 2](#) (Safety laboratory tests: Order of presentation and International system of units) will be presented graphically as described above.

In general, all laboratory data will be listed in by-patient data listings by treatment group, country, patient, laboratory system, laboratory test and visit/relative study day. The associated reference range and any clinically notable criteria will also be presented in the by-patient data listing.

Identification of abnormal laboratory test results

Reference range classification

For each quantitative laboratory test, the result will be classified into one of the mutually exclusive categories based on the individual laboratory reference range as follows:

- Low: Value below the lower limit of normal (LLN).
- Normal: Values within the normal range (\geq LLN to \leq ULN).
- High: Value above the upper limit of normal (ULN).

The change from Baseline at each windowed post-baseline visit will be presented as a shift table for each treatment group and across active bimagrumab treatment groups combined (“Active Total: Safety” - Includes bimagrumab 700 mg, bimagrumab 210 mg and bimagrumab 70 mg), overall and by region.

Percentages (%) will be derived relative to the number (n) of patients “at risk” (in SAF analysis set, or ongoing at the start of follow-up) with laboratory test results available at Baseline and the relevant windowed visit.

Clinically notable criteria

Clinically notable criteria are key laboratory test values. See [Section 3.8](#) (Clinically notable values) for the list of hematology and clinical tests with associated clinically notable criteria. For the list of aforementioned laboratory tests, all scheduled and unscheduled laboratory test results will be evaluated to determine if the result complies with the criterion.

Newly occurring clinically notable criteria

Newly occurring clinically notable criteria will be presented, where clinically notable laboratory values will be considered newly occurring if they are not present at Baseline. If assessments cannot be made at Baseline due to missing value(s), post-baseline values meeting the clinically notable criterion will be considered as newly occurring.

The incidence of patients per laboratory test with at least one newly occurring clinically notable test result on treatment at last infusion of study drug (expected per protocol at Week 20 + 56-days) will be presented by treatment group and across active bimagrumab treatment groups combined (“Active Total: Safety” - Includes bimagrumab 700 mg, bimagrumab 210

mg and bimagrumab 70 mg), overall only. The percentage (%) per laboratory test will be calculated as the number (n) of patients with at least one scheduled or unscheduled newly occurring clinically notable test result occurring after the start of the first infusion of study drug up to and including the last available assessment assigned to treatment relative to the total number of patients “at risk” (in the SAF analysis set).

Similarly, the incidence of patients per laboratory test with at least one newly occurring clinically notable criteria result within the post-treatment follow-up will be presented by treatment group and across active bimagrumab treatment groups combined (“Active Total: Safety” - Includes bimagrumab 700 mg, bimagrumab 210 mg and bimagrumab 70 mg), overall only. The percentage (%) per laboratory test will be calculated as the number of patients with at least one scheduled or unscheduled newly occurring clinically notable criteria within post-treatment follow-up relative to the total number of patients “at risk (ongoing at the start of post-treatment follow-up).

Finally, the incidence of patients per laboratory test with at least one newly occurring clinically notable criteria result in the overall study (entire study period) will also be presented in a similar manner, as described for treatment-emergent and post-treatment follow-up.

Abnormal liver enzyme laboratory values

Abnormal liver function tests such as aspartate aminotransferase (AST), alanine aminotransferase (ALT), alkaline phosphatase (ALP) or total bilirubin (except if accompanying Gilbert’s Disease) are detailed in [Section 3.9](#) (Liver event and laboratory trigger definitions).

Descriptive statistics (see [Section 3.2](#) [Precision and summary statistics]) for abnormal AST, ALT, ALP or total bilirubin will be presented for all patients assigned to the SAF analysis set, at each windowed visit and change from Baseline at each windowed post-baseline visit and End of Treatment (derived)/End of Study (derived) as relevant. All summaries will be presented for each treatment group and across active bimagrumab treatment groups combined (“Active Total: Safety” - Includes bimagrumab 700 mg, bimagrumab 210 mg and bimagrumab 70 mg), overall only.

The incidence of patients per liver enzyme laboratory test (ALT, AST, ALP and total bilirubin) with abnormal values, above certain cut-offs (e.g. ALT > 5x ULN, ALT > 8x ULN etc.), per the Liver safety guidance (Version 2.5), will be presented by treatment-emergent, post-treatment follow-up and study incidence, for each treatment group and across active bimagrumab treatment groups combined (“Active Total: Safety” - Includes bimagrumab 700 mg, bimagrumab 210 mg and bimagrumab 70 mg). The percentage (%) per cut-off criterion will be calculated as the number of patients with at least one scheduled or unscheduled value above the cut-off criterion occurring on treatment (expected per protocol at Week 20 + 56-days) or within post-treatment follow-up relative to the total number of patients “at risk” (SAF analysis set or ongoing at the start of post-treatment follow-up).

Newly occurring clinically notable criteria

Newly occurring clinically notable criteria will be presented in a similar manner as described above. For the table of newly occurring liver enzyme abnormalities see [Table 3.7](#) (Liver event and laboratory trigger definitions).

The incidence of patients per abnormal liver enzyme laboratory test (ALT, AST, ALP and total bilirubin) with at least one newly occurring clinically notable criteria on treatment (at last infusion of study drug expected per protocol at Week 20 + 56-days) will be presented by treatment group and across active bimagrumab treatment groups combined (“Active Total: Safety” - Includes bimagrumab 700 mg, bimagrumab 210 mg and bimagrumab 70 mg), overall only. The percentage (%) per laboratory test will be calculated as the number (n) of patients with at least one scheduled or unscheduled newly occurring clinically notable criteria result occurring after the start of the first infusion of study drug up to and including the last available assessment assigned to treatment relative to the total number of patients “at risk” (in the SAF analysis set). The incidences in the post-treatment follow-up and overall study will be presented in a similar manner, adjusting accordingly.

Liver safety guidance analyses

The following mandatory table and by-patient data listing as required by the latest version of the Liver safety guidance (Version 2.5) will be included in RAP Module 7 (CSR Deliverables):

- Peak post-baseline: Change from Baseline to the highest post-baseline laboratory result by liver function test: ALT, AST, ALP and total bilirubin (see Table 6.2 of Liver safety guidance).
- By-patient data listing of laboratory values of patients with liver events (Listing 6.6 of Liver safety guidance).

In addition, figures will be presented. These will include:

- Box-and-whisker plots (by treatment group and across active bimagrumab treatment groups combined [“Active Total: Safety” - Includes bimagrumab 700 mg, bimagrumab 210 mg and bimagrumab 70 mg]) of /ULN-normalized values.
- Scatter plot of peak post-baseline TBL/ULN-normalized values versus peak post-baseline AST/ULN-normalized values and ALT/ULN-normalized values (Evaluation of Drug-Induced Serious Hepatotoxicity [eDISH] plots) to identify potential Hy’s Law cases.

For further details see [Section 3.2](#) (Graphical displays at the study level) of the latest liver safety guidance (Version 2.5).

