6.5.4 Laboratory evaluations

Bone marker results are influenced by the patients' fasting status. Therefore, it is important to ensure that blood samples for bone marker assessments are collected after **8 hour of fasting** (D1, W12, W24 (EoT)). This fasting status is preferable for the other blood samples as well, but this is not a requirement.

A central laboratory will be used for analysis of all specimens collected [REDACTED]

[REDACTED] Details on the collections, shipment of samples and reporting of results by the central laboratory are provided to investigators in the *Laboratory manual*. Reference to the Laboratory Manual should be made for identification of laboratory reference range values and the schema for notification of site staff and Novartis for out of range values.

Key laboratory test values that are clinically notable are defined in [Appendix 1](#).

All abnormal values will be assessed by the investigator who will decide what action needs to be taken, taking into account the overall status of the patient.

In the case where a laboratory assessment listed in the inclusion/exclusion criteria is outside of a **protocol-specified range** at screening, the assessment may be repeated once for the purpose of inclusion. The repeated result must be within protocol-specified range prior to randomizing the patient. Investigators will have the discretion to record abnormal test findings on the medical history eCRF, whenever in their judgment, the test abnormality occurred prior to the informed consent signature.

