9.5.2.4 Laboratory data

The summary of laboratory measurements by visit will be presented with descriptive statistics (mean, standard deviation, minimum, median, and maximum) for quantitative variables; and with frequency for categorical variables. In addition, change from baseline will be summarized for all parameters to compare post-baseline measurements with corresponding baseline values.

Baseline values will be defined as last non-missing assessment prior to the first dose of study medication. Patients with abnormal laboratory values will be listed and selected parameters will be flagged during study conduct according to pre-defined clinically relevant values. Incidence of abnormalities based on clinically notable criteria will be tabulated.

Newly occurring or worsening liver as well as pancreatic enzyme abnormalities will be summarized.

In addition, all laboratory data will be listed by treatment, patient, and visit and if ranges are available abnormalities will be flagged.

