3.4 Definition of Baseline and post-baseline assessments

Baseline (derived) is defined as the last available assessment (scheduled or unscheduled) prior to the start of the first infusion of study drug, including pre-dose assessments at Day 1. All Day 1 assessments are to be performed prior to the start of the first infusion of study drug with the exception of DXA assessments. The protocol allows a + 2-day window for performing Baseline DXA. Dual energy X-ray absorptiometry (DXA) assessments obtained within the allowed 2-day window following the first infusion of study drug at Day 1 will still be regarded as Baseline assessments.

Assessments performed after the start of the first infusion are considered post-baseline assessments with the exception of DXA assessments, as specified above.

Change from Baseline is derived where both Baseline and post-baseline values are available:

Change from Baseline = (post-baseline value – Baseline value).

Percentage (%) change from Baseline at each post-baseline visit:

Percentage (%) change from Baseline = $(\text{[post-baseline value – Baseline value]}/\text{Baseline value}) \times 100$.

End of Treatment (derived) is defined as the last available assessment (scheduled or unscheduled) assigned to treatment (expected per protocol at Week 20 + 56-days).

End of Study (derived) is defined as the last available assessment (scheduled or unscheduled) assigned to the study.

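### SAP 2.11.7 analyses lipase on fasting samples only, although the protocol does not require fasting for lipase, so valid results drop out of the by-visit, change, plot and shift summaries

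*SAP*

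**What the plan says.** SAP 2.11.7 begins from a general premise: "Blood samples should be recorded after an 8-hour fast". It then says that fasting status (yes/no) is recorded at sample collection and sets the rule: "For the following laboratory tests sensitive to fasting status, only fasting results will be used for analysis purposes". The tests listed are glucose, cholesterol, lipids and lipase.

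Protocol 6.5.4 is narrower. It makes the 8-hour fast mandatory for bone-marker samples at Day 1, Week 12 and Week 24, and adds: "This fasting status is preferable for the other blood samples as well, but this is not a requirement".

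Protocol 9.5.2.4 attaches no fasting condition to the laboratory analysis. On Baseline: "Baseline values will be defined as last non-missing assessment prior to the first dose of study medication". On change: "In addition, change from baseline will be summarized for all parameters to compare post-baseline measurements with corresponding baseline values".

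SAP 2.14, which lists departures from the protocol's planned analysis, does not mention the lipase restriction.

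**The concern.** The SAP excludes lipase results that the protocol allows sites to collect and plans to summarise. Its premise of a general fast is not what the protocol requires.

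Lipase is not an incidental analyte here. Protocol 3.6 describes dose-dependent, transient rises in lipase and/or amylase seen in several earlier studies and adds monitoring so that the finding can be evaluated. Amendment 4 introduced that monitoring. Under the SAP rule, the lipase summaries describe a subset selected by fasting status while the amylase summaries use every result. Two enzymes that are meant to be read together may therefore rest on different samples and different patients.

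**Working it through.** The documents give no figure to reproduce and no fasting rate, so the check compares sections and counts scheduled visits.

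**Step 1: lipase draws against the mandated fast.** Protocol Table 6-3 schedules clinical chemistry, including lipase, at six visits. Protocol 6.5.4 gives the visits with a mandated fast.

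| Lipase draw | Fast mandated at that visit? |
|---|---|
| Screening | No |
| Week 4 | No |
| Week 8 | No |
| Week 12 | Yes (bone markers) |
| Week 24 | Yes (bone markers) |
| Week 48 | No |

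Under a mandated fast: 2 of 6. With no mandated fast: 6 − 2 = 4 of 6.

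**Step 2: Baseline.** The third mandated-fast visit is Day 1, but Protocol Table 6-1 has no chemistry sample on Day 1. That fast therefore does not protect the lipase Baseline, which normally comes from Screening.

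**Step 3: which outputs the rule reaches.**
- By-visit summaries (SAP 2.11.7): a non-fasting result is not used at its visit.
- Change from Baseline (SAP 3.4): "Change from Baseline is derived where both Baseline and post-baseline values are available". An unusable Baseline removes every change value for that patient.
- Mean-change plot (SAP 2.11.7): "Only laboratory assessments with a clinically notable criterion as defined in" SAP 3.8 are plotted. Lipase has such criteria in Table 3.6, so it is plotted and the rule applies.
- Shift table (SAP 2.11.7): the denominator is patients "with laboratory test results available at Baseline and the relevant windowed visit", so both results are needed.

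**Step 4: loss per patient.** SAP Table 3.3 gives five windowed post-baseline chemistry visits: Weeks 4, 8, 12, 24 and 48. Change rows = 5 + End of Treatment (derived) + End of Study (derived) = 7.
- No fasting pre-dose lipase result: 0 of 5 shift visits and 0 of 7 change rows remain, even if Weeks 12 and 24 were fasting.
- Fasting Baseline but one non-fasting post-baseline visit: only that visit is lost.

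**Step 5: unscheduled re-checks.** Protocol Table 7-2 calls for enzymes to be re-checked at 3 × ULN or above and states no fasting condition. Under SAP 3.5.1 unscheduled results enter the visit windows, and they can supply the derived End of Treatment and End of Study rows. A non-fasting re-check would be excluded from these summaries.

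**Step 6: clinically notable counts.** SAP 2.11.7 evaluates all scheduled and unscheduled results against the criteria, and Table 3.6 puts a fasting qualifier on glucose but not on lipase. These counts are therefore probably unfiltered, but the SAP does not say that they are exempt from the fasting rule. It also does not say whether a non-fasting pre-dose lipase value counts as a Baseline. If it is treated as missing, the SAP's missing-Baseline rule would class a notable lipase value as newly occurring even when it was already present before dosing.

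**The case against.** The strongest reply is that this is a pre-specified analytic judgement, applied alike to all arms. The SAP classes lipase as fasting-sensitive and amylase as not, and nothing in the documents shows that to be wrong. Protocol Section 9 leaves analysis detail to the SAP. Tolerating non-fasting samples at collection does not oblige anyone to analyse them, and lipase still receives a change summary. That the sponsor may hold this view stands, which is why a fasting-only display should be kept. It does not explain why the main safety summary should discard protocol-compliant results, and neither document gives a reason specific to lipase.

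The reply also questions the size of the problem, with good reason:
- Table 6-3 lists fasting glucose on the same panel as lipase, and Protocol Section 6 advises early laboratory work. Many samples may be fasting even where no fast is mandated, so 4 of 6 counts unprotected draws and is not a rate of non-fasting samples.
- Screening assessments may be repeated (Protocol 3.1), so a fasting repeat could supply Baseline.
- The SAP's own Baseline definition carries no fasting condition. A programmer could leave Baseline unfiltered, which would avoid the whole-patient loss but would set aside the fasting rule for half of each change value.
- The two derived rows will often repeat Week 24 and Week 48, so the 7 change rows are not 7 separate pieces of information.
- The notable-value tables, which carry most of the pancreatic safety question, are probably unaffected.

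These points limit the consequence. They leave the conflict between SAP 2.11.7 and Protocol 6.5.4 and 9.5.2.4 in place.

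**Conclusion.** The concern holds. Read as written, SAP 2.11.7 removes non-fasting lipase results from the by-visit, change, plot and shift summaries, although the protocol does not require fasting for lipase and plans Baseline and change for all parameters.

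The size can be stated only as counts: 4 of 6 scheduled lipase draws have no mandated fast, and a patient without a fasting pre-dose result loses 5 of 5 shift visits and 7 of 7 change rows. The latter assumes the fasting rule applies to Baseline as well as to post-baseline results. The number of patients affected cannot be derived from the documents.

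The affected tables are descriptive, and no direction or between-arm bias is claimed. Amylase summaries, by-patient listings, adverse event reporting and site monitoring are unaffected. The change should be made because lipase belongs to a named safety finding and the correction is cheap.

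**What to change.** In SAP 2.11.7:

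1. Remove lipase from the fasting-only list, so that its Baseline and its by-visit, change, plot, shift and notable-value outputs use all results, as for amylase.
2. State that the clinically notable and newly occurring lipase counts use all scheduled and unscheduled results, and that newly occurring is judged against the last pre-dose result whatever its fasting status.
3. Flag fasting status in the listings and add a fasting-only lipase summary as a sensitivity display.

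The cost is a short SAP text change, one program filter and one extra display. No new data are needed, because fasting status is already recorded. The downside is that the main summary may carry some fasting-related variability, which the sensitivity display would show.

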In general, all vital signs data will be listed in by-patient data listings by treatment group, country, patient and visit/relative study day. Any clinically notable criteria will also be presented in by-patient data listing.

Abnormal vital signs changes

Abnormal vital signs criteria can be found in [Table 3.6](#) (Clinically notable laboratory values, vital signs, ECG intervals and echocardiography).

Newly occurring clinically notable criteria

Newly occurring clinically notable criteria will be presented in a similar manner as described in [Section 2.11.7](#) (Laboratory data). As before, if assessments cannot be made at Baseline due to missing value(s), post-baseline values meeting the clinically notable criterion will be considered as newly occurring.

The incidence of patients per vital sign (SBP [mm Hg], DBP [mm Hg], pulse rate [bpm] and weight [kg]) with at least one newly occurring clinically notable criteria on treatment (at last infusion of study drug expected per protocol at Week 20 + 56-days) will be presented by treatment group and across active bimagrumab treatment groups combined (“Active Total: Safety” - Includes bimagrumab 700 mg, bimagrumab 210 mg and bimagrumab 70 mg), overall only. The percentage (%) per vital signs test will be calculated as the number (n) of patients with at least one scheduled or unscheduled newly occurring clinically notable criteria result occurring after the start of the first infusion of study drug up to and including the last available assessment assigned to treatment relative to the total number of patients “at risk” (in the SAF analysis set). The incidences in the post-treatment follow-up and overall study will be presented in a similar manner, adjusting accordingly.

All newly occurring clinically notable vital signs data will be listed by treatment group, country, patient, and visit with abnormal values flagged.

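### Percentages of newly occurring notable safety values use denominators that include patients already abnormal at Baseline, and the follow-up table, read literally, counts persisting on-treatment abnormalities again

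*SAP*

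**What the plan says.** SAP 2.11.7 uses Baseline as the only reference: "clinically notable laboratory values will be considered newly occurring if they are not present at Baseline". A missing Baseline is resolved in favour of counting: "If assessments cannot be made at Baseline due to missing value(s), post-baseline values meeting the clinically notable criterion will be considered as newly occurring".

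The on-treatment numerator is patients with at least one such result "up to and including the last available assessment assigned to treatment relative to the total number of patients" at risk, and at risk is glossed as those "in the SAF analysis set". SAP 2.7 defines that set as everyone who received at least one infusion.

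For follow-up, SAP 2.11.7 counts patients with "at least one scheduled or unscheduled newly occurring clinically notable criteria within post-treatment follow-up relative to the total number of patients" at risk, which here means those ongoing at the start of post-treatment follow-up. The definition of new is not restated for this period. A third table covers the entire study period.

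The rule carries over to liver enzymes (2.11.7), vital signs (2.11.8), ECG (2.11.9) and echocardiography (2.11.10). For vital signs the instruction on later periods is only: "The incidences in the post-treatment follow-up and overall study will be presented in a similar manner, adjusting accordingly".

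Protocol 9.5.2.4 asks for slightly more: "Newly occurring or worsening liver as well as pancreatic enzyme abnormalities will be summarized".

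**The concern.** A patient who meets a criterion at Baseline can never be newly abnormal on it. Keeping that patient in the denominator turns an incidence among patients at risk into a smaller number under the same label. A patient with no result in the period has the same effect. If Baseline abnormality differs between arms, the dilution differs too, so equal risks can print as unequal percentages.

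Follow-up raises a separate problem. If new means only absent at Baseline, an abnormality that began on drug and is still present after it is tabulated in both periods. A reader could then take carry-over of an on-drug effect for harm that began after treatment stopped.

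Finally, the SAP definition has no worsening rule, although the protocol names worsening, and the list of changes in SAP 2.14 does not mention the difference.

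**Working it through.** The documents state no figure on this point, so there is none to reproduce. The check has three parts.

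**1. Where Baseline abnormality is possible.** Protocol 4.2 entry limits against the criteria in SAP Table 3.6 (section 3.8):

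| Measure | Excluded at entry | Notable criterion | Present at Baseline? |
|---|---|---|---|
| Hemoglobin | < 8.0 g/dL | < 8.0 g/dL | about nil |
| Platelets | < 75,000/mm³ | < 75 × 10⁹/L | about nil |
| eGFR | < 30 mL/min | < 30 mL/min | about nil |
| ALT, AST | > 3 × ULN | > 3 × ULN | about nil |
| Weight loss ≥ 5%; BP, pulse or QTc change | – | change from Baseline | no, by construction |
| Hemoglobin | < 8.0 g/dL | < LLN | possible |
| Albumin, pre-albumin | no limit | < LLN | possible |
| SBP | > 180 mmHg | > 150 mmHg | possible |
| DBP | > 100 mmHg | > 90 mmHg | possible |
| QTcF | ≥ 500 msec, with exceptions | ≥ 450 (men) / ≥ 460 (women) msec | possible |
| HbA1c | ≥ 8.5% | ≥ 7.5% | possible |

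**2. Dilution of the on-treatment percentage.** Let b be the share meeting the criterion at Baseline and r the risk among the rest. The printed percentage is r × (1−b); among patients at risk it is r. If a share m of those at risk also have no result in the period, the factor becomes (1−b)(1−m). The documents give neither b nor m. With r = 20% and m = 0, both assumed:

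| b | Printed | Among patients at risk |
|---|---|---|
| 0% | 20.0% | 20% |
| 5% | 19.0% | 20% |
| 10% | 18.0% | 20% |
| 20% | 16.0% | 20% |
| 30% | 14.0% | 20% |
| 50% | 10.0% | 20% |

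Two arms with the same 20% risk but b = 20% and 30% would print 0.20 × 0.80 = 16% and 0.20 × 0.70 = 14%.

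**3. Repeat counting in follow-up.** Take b = 0, as for weight loss. Let q be the on-treatment incidence, s the share of those patients still (or again) abnormal in follow-up, and f the risk of first onset in follow-up among patients not yet abnormal. The literal rule prints q·s + (1−q)·f. With q = 20% and f = 5%, again assumed:

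- s = 0: 0 + 0.80 × 0.05 = 4.0%
- s = 25%: 0.05 + 0.04 = 9.0%
- s = 50%: 0.10 + 0.04 = 14.0%
- s = 100%: 0.20 + 0.04 = 24.0%

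First onset among patients not yet abnormal is 5.0% in every row. The excess is q·s, and it vanishes if on-treatment abnormalities resolve before follow-up.

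Weight is the concrete case. Protocol 3.6 reports net weight loss on bimagrumab in other studies, Protocol Table 6-1 schedules weight at Weeks 36 and 48, and SAP 2.11.8 includes weight in these tables.

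The SAP is stricter elsewhere. The laboratory shift tables in 2.11.7 require a result at Baseline and at the visit, and 2.11.1 assigns adverse events to the post-treatment period by date of onset or worsening.

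**The case against.** The strongest reply is that at risk is a defined term. SAP 2.4.1 uses it, unless otherwise specified, for patients who entered the epoch, and adverse events use the same base. A proportion of the safety set is a disclosed descriptive summary applied alike in every arm. That stands. It would be tempting to infer that both percentages are simply wrong, or that both use the whole safety set. The documents do not support either reading: the follow-up base is patients ongoing at the start of follow-up, and the fault is in the label and the dilution.

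Dilution is also about nil for much of Table 3.6. No prevalence is given for the remaining criteria, so a claim that they are common early after hip surgery would be an assumption. Imbalance effects are small beside sampling error. For 16% against 14% with 70 per arm, the 95% half-width is 1.96 × √(0.16×0.84/70 + 0.14×0.86/70) = about 12 points, against a 2-point artefact. No test is planned on these percentages in 2.11.7.

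On follow-up, SAP 2.3 extends its treatment-emergent conventions to assessments with notable criteria, and the adjusting wording leaves room for an onset-based reading. But 2.3 states its onset rule for adverse events only, and no sentence applies it to measured values. Two programmers could produce different tables. The reach is limited: in follow-up, safety laboratory tests are scheduled only at Week 48 and no ECG is scheduled.

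A reader might also infer that the SAP drops worsening altogether. It does not. Liver tests have graded cut-offs and a peak-change table (2.11.7), and lipase and amylase have two tiers, above 2 × and at least 3 × ULN (Table 3.6). Worsening within a pancreatic tier is what those tables miss. Shift tables and listings help for laboratory tests, but vital signs have a shift table only for BMI category and ECG has none specified.

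**Conclusion.** The point holds in a limited form. Both denominators include patients who cannot become newly abnormal and patients with no result in the period, so the printed figure understates the risk among patients truly at risk by the factor (1−b), or more where results are missing. The direction follows from the text. The size does not, because b is not given: 19% for a 20% risk at b = 5% and 14% at b = 30% are assumed illustrations. The effect is confined to criteria looser than the entry limits or without one.

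Repeat counting in follow-up follows from the literal definition but depends on persistence or recurrence and on how an ambiguous text is programmed. The overall-study table counts each patient once per test and is not affected by it. A claim that the tables will show false drug effects goes further than the documents allow. These are descriptive safety tables, and no tested endpoint changes.

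**What to change.** In SAP 2.11.7 to 2.11.10:

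- **Denominator.** For each criterion and period, use patients who do not meet the criterion at Baseline (or whose Baseline is missing, as the SAP already allows) and who have at least one result in that period.
- **Follow-up.** Count a value as newly occurring only if the criterion was absent at Baseline and throughout treatment, and show persisting on-treatment abnormalities in a separate row. Alternatively, keep the programming and relabel the table as present in follow-up, not present at Baseline.
- **Worsening.** Add a worsening-from-Baseline row for lipase and amylase to match Protocol 9.5.2.4. Liver tests are already largely covered by the graded cut-off and peak-change tables.

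The cost is a few sentences of SAP text plus a denominator, a flag and a row in tables already planned. No new data are needed.
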